10.4.3 Analysis of the Secondary and Exploratory Endpoints

- Per-protocol evaluation of PPI deprescribing on post-TIPS HE: Statistical analysis will be conducted via a two-sided unpaired T-test of the hypothesis $H_0: \mu_{+PPI} = \mu_{-PPI}$ versus $H_1: \mu_{+PPI} \neq \mu_{-PPI}$. Here μ_{+PPI} and μ_{-PPI} are the pre to post-TIPS change in PHES estimated from the sample means in the per-protocol dataset.
- ITT analysis of the change in CLDQ and QOLRAD scores: Statistical analysis will be conducted via a two-sided unpaired T-test of the hypothesis $H_0: \mu_{+PPI} = \mu_{-PPI}$ versus $H_1: \mu_{+PPI} \neq \mu_{-PPI}$. Here μ_{+PPI} and μ_{-PPI} are the pre to post-TIPS change in QOL scores on the respective surveys, estimated in the ITT dataset.
- Episodes of overt HE: Statistical analysis will be conducted via a two-sided Fisher's exact test of the hypothesis $H_0: p_{+PPI} = p_{-PPI}$ versus $H_1: p_{+PPI} \neq p_{-PPI}$. Here p_{+PPI} is the proportion of patients in the PPI continuation arm experiencing at least one episode of

greater than or equal to West-Haven grade 2 overt HE, and p_{+PPI} is the corresponding proportion in the PPI discontinuation arm.

- On-demand requirement for acid suppression therapy: The proportion of patients in the PPI discontinuation arm needing on-demand histamine H2 blockers and PPIs will be reported.
- Adverse events: Statistical analysis will be conducted via a two-sided Fisher's exact test of the hypothesis $H_0: p_{+PPI} = p_{-PPI}$ versus $H_1: p_{+PPI} \neq p_{-PPI}$. Here p_{+PPI} is the proportion of patients in the PPI continuation arm experiencing at least AE, and p_{-PPI} is the corresponding proportion in the PPI discontinuation arm.
- Exploratory analysis of the role of the GI tract microbiome in mediating PPI induced post-TIPS HE: Analysis will be conducted using statistical mediation analysis (34, 43). Criteria for assessing mediation are based on the following equations:

$$Y = \mu_1 + c X + \varepsilon_1$$

$$M_j = \mu_2 + a X + \varepsilon_2$$

$$Y = \mu_3 + c' X + b M_j + \varepsilon_3$$

Here Y is a vector where the i^{th} element represents the pre to post-TIPS change in PHES for the i^{th} patient. M_j is a vector describing the bacterial abundance for the j^{th} taxon with the i^{th} element representing the pre to post-TIPS change for the i^{th} patient. X is an indicator vector where the i^{th} element is 0 if the patient was randomized to the PPI discontinuation arm and 1 otherwise. The μ and ε terms represent intercepts and error terms, respectively. Variable M_j is considered a mediator if the regression coefficients satisfy (1) $c \neq 0$, (2) $a \neq 0$, and (3) $b \neq 0$. The non-parametric bootstrap test of Preacher and Hayes will be utilized to formally test these relationships (34). For microbiome studies, the mediating effects on HE are analyzed using relative abundances of bacterial taxa at the family and genus levels in a causal compositional mediation model (43). Due to the multiplicity of bacterial families and genera, the false discovery rate will be used for multiple testing correction (44).

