4.2.2 Secondary Endpoints

Secondary endpoints of the study will include a per-protocol analysis of the change in PHES pre versus post-TIPS in the PPI continuation versus discontinuation arm; an ITT analysis of the change in CLDQ and QOLRAD scores pre versus post-TIPS in the PPI continuation versus discontinuation arms; episodes of overt HE, defined as a West-Haven score greater than or equal to 2 (e.g. gross disorientation, drowsiness, asterixis, and inappropriate behavior), on-demand use of histamine H2 blockers or PPIs due to GERD symptoms, and AEs.

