7.5 Concomitant Medications, Treatments, and Procedures

All concomitant standard of care medications for post-TIPS HE (e.g. lactulose, rifaximin) deemed necessary by gastroenterology and IR physicians will be permitted. Use of such medications will be documented on case report forms (CRFs).

For GERD symptoms related to discontinuation of PPIs, patients will be encouraged to undertake lifestyle interventions (e.g. smoking cessation, avoiding late evening meals, and head-of-the-bed elevation) (40). If lifestyle interventions are inadequate to control GERD symptoms, patients may use on-demand over-the-counter histamine H2 blocker therapy. On-demand use of PPIs will be discouraged but permitted for refractory, intolerable GERD symptoms. Use of on-demand pharmacological agents will be recorded on the CRFs.

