10.2 Statistical Hypotheses

Primary endpoint: The null hypothesis is that there is no difference between PPI continuation and discontinuation groups in the change in PHES pre versus post-TIPS. The alternative hypothesis is that there is a difference in the change in PHES pre versus post-TIPS in the PPI continuation and discontinuation groups:

$$H_0: \mu_{+PPI} = \mu_{-PPI} \text{ versus } H_1: \mu_{+PPI} \neq \mu_{-PPI}$$

Here μ_{+PPI} represents the mean difference in PHES among patients in the PPI continuation arm, and μ_{-PPI} represents the mean difference in PHES among patients in the PPI discontinuation arm.

Secondary endpoints:

- Per-protocol evaluation of PPI deprescribing on post-TIPS HE: The null hypothesis is that there is no difference in the change in PHES among patients who adhered with PPI discontinuation instructions versus those who continued to use PPIs.
- ITT analysis of the change in CLDQ and QOLRAD scores: The null hypothesis is that there is no difference in the pre to post-TIPS change in CLDQ/QOLRAD scores among patients in the PPI discontinuation arm compared to patients in the PPI continuation arm.
- Episodes of overt HE: The null hypothesis is that there is no difference in the number of patients experiencing an episode of overt HE, defined as a West-Haven score greater than or equal to 2, in the PPI discontinuation arm compared to patients in the PPI continuation arm.
- On-demand requirement for acid suppression therapy: Descriptive statistics will be presented on the number of patients in the PPI discontinuation arm reporting on-demand use of histamine H2 blockers or PPIs.
- Adverse events: The null hypothesis is that there is no difference in the number of patients experiencing an AE in the PPI discontinuation arm compared to patients in the PPI continuation arm.

Exploratory endpoints:

For analyses exploring the role of the microbiome in mediating PPI induced post-TIPS HE, the null hypothesis is that $b = 0$ and that $c = c'$ (no mediation, see Figure 2). The alternative hypothesis is that $b \neq 0$ and $c' < c$ (partial or complete mediation) (34).

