10.4.5 Adherence and Retention Analyses

Analysis of on-demand acid suppression pharmacotherapy will be performed as described above in Section 10.4.3. No retention analyses are planned.

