10.6.3 Breaking the Study Blind/Participant Code

Not applicable.

11 Source Documents and Access to Source Data/Documents

Source data will include CRFs and the electronic medical record. CRFs will include Duke medical record number, a study subject identifier, PHES test results, QOL survey results, and patients' reported use of on-demand histamine H2 blockers and PPIs. Raw source data and post-processed data from stool microbiome sequencing will be maintained in the Duke Protected Analytics Computing Environment (PACE).

12 Quality Assurance and Quality Control

Quality control procedures will be implemented beginning with the data entry into CRFs. Any missing data or data anomalies will be reviewed by the PI and will be communicated to study members for clarification/resolution. The study team will provide direct access to all trial related source data/documents and reports for the purpose of monitoring and auditing by the IRB.

13 Ethics/Protection of Human Subjects

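### The only planned adherence analysis counts on-demand acid suppression in one arm, so it does not show how many patients stopped their PPI

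*Combined protocol and SAP*

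**What the plan says.** The document is the whole analysis plan; section 10.1 states that no separate SAP will be written.

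- **Adherence section (10.4.5):** "Analysis of on-demand acid suppression pharmacotherapy will be performed as described above in Section 10.4.3. No retention analyses are planned". Nothing else is named as an adherence measure.
- **The analysis it points to (10.4.3):** "The proportion of patients in the PPI discontinuation arm needing on-demand histamine H2 blockers and PPIs will be reported". It is descriptive and covers one arm.
- **The same item in 10.2:** "the number of patients in the PPI discontinuation arm reporting on-demand use of histamine H2 blockers or PPIs".
- **The endpoint (4.2.2):** "on-demand use of histamine H2 blockers or PPIs due to GERD symptoms".
- **What on-demand PPI use means (7.5):** "On-demand use of PPIs will be discouraged but permitted for refractory, intolerable GERD symptoms". Sections 7.1.1 and 7.5 offer H2 blockers to the discontinuation arm as the route for GERD symptoms that lifestyle measures do not control.
- **Data capture (section 11):** the CRF contents listed include patients' "reported use of on-demand histamine H2 blockers and PPIs".
- **Per-protocol groups (10.3):** patients count as having discontinued if their on-demand H2-blocker or PPI use was below two times a week, and as having continued if they took a daily PPI dose at or above the omeprazole 20 mg equivalent. Section 10.4.3 uses these groups for a t-test of PHES change.

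**The concern.** The intervention is an instruction to stop a drug, given open-label. How many patients stopped is therefore the fact needed to interpret the ITT contrast. The sample size argument in 10.5 assumes that test performance is unchanged across the whole discontinuation arm, with no allowance for patients who stay on a PPI.

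The reported figure answers a different question: how many patients needed symptom relief. Three kinds of complete failure to stop lie outside its wording: never stopping, returning to a scheduled PPI, and receiving a PPI for a reason other than GERD. The last is foreseeable, since section 2.1 notes that short PPI courses are indicated for ulcer disease and 7.1.2 has every patient admitted after TIPS. Meanwhile a patient who did as told and used only an H2 blocker is counted alongside PPI users.

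A null PHES result could then be read as showing that stopping PPIs does not help when many patients had not stopped, and the plan commits to no output that would separate the two.

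**Working it through.** **Plan's own figure.** The documents give no expected or target adherence rate, so there is none to reproduce. The related stated figure is power of 71% to 96% with 20 per arm (10.5). It cannot be rebuilt forward because no SD or standardized effect is given; it is back-solved in step 2.

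**Step 1: what the planned figure counts.** In a discontinuation arm of 20, let these groups not overlap:

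- k = PPI users outside the on-demand wording (never stopped, resumed scheduled use, or non-GERD reason)
- p = on-demand PPI users
- h = users of on-demand H2 blockers only

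Then:

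- planned pooled figure = (p + h)/20
- its PPI component = p/20
- true PPI use = (k + p)/20
- PPI component minus true = −k/20, which is −5 percentage points per uncounted patient
- pooled figure minus true = (h − k)/20, which can take either sign

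The counts below are assumed, for illustration:

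| k | p | h | Planned pooled | PPI component | True PPI use | Pooled minus true |
|---|---|---|---|---|---|---|
| 4 | 0 | 0 | 0% | 0% | 20% | −20 points |
| 4 | 2 | 0 | 10% | 10% | 30% | −20 points |
| 8 | 2 | 2 | 20% | 10% | 50% | −30 points |
| 4 | 2 | 4 | 30% | 10% | 30% | 0 |
| 4 | 2 | 6 | 40% | 10% | 30% | +10 points |
| 2 | 2 | 8 | 50% | 10% | 20% | +30 points |

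The fourth row agrees with the truth only because four H2-only users happen to replace four uncounted PPI users.

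**Step 2: why the number of stoppers matters.** Inputs are n = 20 per arm, two-sided alpha 0.05 (10.4.1), and power of 71% and 96%. Solving power = P(T > t₀.₉₇₅,₃₈), where T is noncentral t with 38 degrees of freedom and noncentrality d√(20/2), gives d = 0.816 and d = 1.204 (normal approximation: 0.795 and 1.173). If k patients in the discontinuation arm stay on a PPI and gain nothing, the ITT effect becomes d(1 − k/20). The documents give no rate, so k runs over an assumed range of 0 to 10:

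| k of 20 | Diluted d | Power |
|---|---|---|
| 0 | 0.816 to 1.204 | 71% to 96% |
| 2 | 0.734 to 1.084 | 62% to 92% |
| 4 | 0.652 to 0.963 | 52% to 84% |
| 6 | 0.571 to 0.843 | 42% to 74% |
| 10 | 0.408 to 0.602 | 24% to 46% |

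This loss comes from non-adherence itself, not from how adherence is reported. The reporting matters because k, which drives the loss, is the quantity that the planned analysis leaves out.

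**Step 3: whether 10.3 supplies the count.** It sorts patients by actual use, but three gaps remain. No tabulation of the groups by randomized arm is planned. The rule for having discontinued looks only at on-demand use, so a scheduled daily user with no on-demand use meets both definitions if they are read literally. A patient using on-demand agents two or more times a week but below the daily dose meets neither.

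**The case against.** The strongest reply is that the plan already analyses actual use. Section 10.2 compares patients who adhered with those who continued, 10.3 would place a full-dose daily user among the continuers, and 10.4.3 tests PHES change in those groups. Setting ITT beside per-protocol goes some way towards asking whether stopping failed or patients failed to stop. This stands in part: a reader might infer that non-stoppers are invisible to the whole plan, and 10.3 shows that they are not. But the per-protocol item is an efficacy test, and no count of stoppers by arm is planned from it.

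A reader might also infer that regular PPI use will not be recorded. The documents do not support that. The section 11 list is not complete: 7.5 adds HE medications to the CRF and 8.3 adds adverse events, and neither is in that list. The electronic record is also named as source data, and 10.3 presupposes data on daily dose. What remains is that no passage names the field or reports from it.

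Non-adherence by a participant would also be a protocol deviation under 14.3. That is a route for individual reports, not an analysis.

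It is tempting to say that the planned figure always understates failure to stop. That is certain only for its PPI component; the pooled figure exceeds true PPI use whenever h is greater than k.

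Finally, on-demand need is a reasonable description of tolerability, QOLRAD measures reflux burden separately, and nothing prevents the two drug classes from being shown apart. All of this is fair, but none of it makes the pooled figure a measure of stopping.

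**Conclusion.** The point holds in this form: followed as written, the plan's only adherence analysis does not measure PPI stopping. Its PPI component is too low by 5 percentage points for each uncounted user in 20, and the pooled figure is off by (h − k)/20 in either direction. Both results follow from the definitions; the particular counts shown are assumptions.

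The primary ITT estimate and its test do not change, and a reader should not infer that they are biased by this wording. What suffers is the reported adherence and the interpretation of a null ITT result. The power figures rest on three assumptions: the effect sizes implied by the stated power, no benefit in patients who stay on a PPI, and full benefit in the rest. The change is worth making because the quantity is central to a deprescribing trial and cheap to obtain.

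**What to change.** In 4.2.2, 10.4.3 and 10.4.5, replace the single proportion with two items, each reported for both arms:

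1. Any PPI use after randomization, whatever the reason or prescriber, split into never stopped, resumed regular use, and on-demand use. In the control arm, the number who stopped follows from the same data; the current plan does not report it, although it also dilutes the contrast.
2. H2-blocker use, shown separately.

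In section 11, name CRF fields for regular PPI agent, dose and days per week in both arms, checked against the electronic record. Reword the 10.3 rule for having discontinued so that it refers to all PPI use, not on-demand use alone, and the groups can be formed from actual use.

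The cost is a small addition to the CRF, filled in at the existing reminder contacts and the final visit. The control arm receives no reminder contacts, so its data must come from the final visit and the record. Reported adherence may look less favourable.

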In addition to better establishing causality and better assessing the potential benefits and risks of deprescribing PPIs to prevent HE, the proposed prospective, randomized study design will allow further analyses to dissect the role of the GI tract microbiome in HE. The proposed study seeks to further evaluate the role of the GI tract microbiome via statistical mediation analysis as illustrated in Figure 2 (34). Scenario A depicts a direct effect of PPIs on HE. Scenario B depicts simple mediation. The microbiome is considered a mediator if (1) PPIs are causally related to HE (i.e. $c \neq 0$ in scenario A), (2) PPIs are causally related to microbiome change (i.e. $a \neq 0$ in scenario B), and (3) the microbiome significantly predicts HE after controlling for PPI use (i.e. $b \neq 0$ in scenario B). Complete mediation is said to occur if $c' = 0$ (i.e. the impact of PPI use on HE is driven entirely through changes in the microbiome), whereas partial mediation is said to occur if $c' \neq 0$ (i.e. PPIs affect the risk of HE both through the microbiome but also through other unexplained mechanisms, such as a direct effect of pH). Formal statistical methods for quantifying such relationships in mediation analysis have been described (34).

Figure 2: Arrows demonstrate directionality of hypothesized causal chains linking PPI use, the microbiome, and post-TIPS HE.

Rationale for a deprescribing trial

This protocol proposes a randomized deprescribing study design, whereby patients who are already taking PPIs are randomized to continue or discontinue their PPI. Because currently available retrospective data suggest PPIs may increase risk of HE, it would be potentially unethical to administer PPIs to patients not already on these agents. In contrast, a deprescribing trial, where patients are randomized to continue or discontinue a potentially ineffective or harmful medication, can be considered in such circumstances (35). Such deprescribing trials are well accepted in the field of geriatrics to combat polypharmacy and reduce pill burden, and PPIs have been the focus of multiple deprescribing trials (29).

Rationale for studying TIPS patients

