10.4 Description of Statistical Methods

10.4.1 General Approach

- For descriptive statistics, such as patient demographics, means and ranges will be reported for continuous variables, whereas counts and percentages will be reported for categorical variables.
- For inferential tests, differences in sample means will be assessed by two-sided unpaired T-tests, whereas differences in proportions will be assessed by two-sided Fisher's exact tests.
- For statistical mediation analysis, the non-parametric bootstrap method of Preacher and Hayes will be utilized (34).
- For all inferential tests, a two-sided p-value less than 0.05 will be considered significant.

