10.5 Sample Size

The target sample size is estimated to provide statistical power for the primary outcome, the pre to post-TIPS change in PHES compared between the PPI continuation and discontinuation groups. Compared to pre-TIPS, patients perform approximately 18%, 51%, 26%, and 48% worse post-TIPS on the number connection A/B, digit symbol, and block design tests, respectively (46). Assuming a similar degree of PHES worsening pre- versus post-TIPS among the PPI continuation arm, but that cessation of PPIs would improve HE such that test performance is unchanged in the discontinuation arm, the estimated power with 20 patients in each arm (40 patients total) would be 71% to 96%. The proposed sample size and study duration are commensurate with previous studies. For example, previous clinical trials of lactulose and rifaximin for minimal HE randomized 61 patients for 12 weeks (47) and 42 patients for 8 weeks (48). Approximately 30 patients undergo elective TIPS creation per year at Duke University Hospital, with approximately 60-75% of those taking PPIs. Thus, approximately 20 patients per year are expected to be eligible for the study.

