10.6 Measures to Minimize Bias

10.6.1 Enrollment/Randomization/Masking Procedures

Randomization codes will be generated and maintained by the PI. Randomization of subjects between the PPI continuation and discontinuation groups will be performed in a 1:1 fashion. The patient and treating IR physician will not be blinded (open-label design). The CRC performing MHE assessments via PHES tests and QOL assessments via the CLDQ and QOLRAD surveys will be blinded to patient assignment.

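### The mediator rule in Section 10.4.3 adds a non-zero total effect that Section 10.2 does not ask for; if that is tested at 0.05, the primary contrast caps detection for every taxon, at a cost that depends on the total effect

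*Combined protocol and SAP*

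**What the plan says.** Section 10.4.3 sets out three regressions: change in PHES on arm (coefficient c), change in a taxon on arm (a), and change in PHES on arm and taxon together (c' and b). A taxon "is considered a mediator if the regression coefficients satisfy" c ≠ 0, a ≠ 0 and b ≠ 0. The rationale in Section 2.2 uses the same three conditions, beginning "The microbiome is considered a mediator if (1) PPIs are causally related to HE". Section 10.4.3 continues: "The non-parametric bootstrap test of Preacher and Hayes will be utilized to formally test these relationships". It then names a compositional mediation model for relative abundances at family and genus level, with false discovery rate correction.

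Section 10.2 frames the hypotheses differently. The null is b = 0 and c = c'; the alternative is b ≠ 0 and c' < c. Nothing there requires c itself to be non-zero.

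Section 10.4.1 sets the level: "For all inferential tests, a two-sided p-value less than 0.05 will be considered significant". Section 10.4.11 labels the mediation work exploratory and attributes its low power to the sample size and to multiple testing. It does not mention the condition on c.

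**The concern.** The plan holds two rules for declaring a mediator, and the named test does not carry out the stricter one. The bootstrap method cited is for the indirect effect (the title of the reference in Section 17 says as much). It gives one result for a×b, not separate results for c, a and b. The plan does not say whether c must be significant first, or which p-value goes into the false discovery rate step.

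The total effect c is the arm difference in change in PHES, which is the primary contrast of Section 10.4.2, and it is the same for every taxon. If condition (1) is applied as a 0.05 test, one missed primary result closes the mediation question for all families and genera, whatever a and b show. That would be an avoidable loss in a small study, on top of the two limits the plan already admits.

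**Working it through.** **Inputs from the documents.** Two-sided 0.05 (Section 10.4.1). Allocation "will be performed in a 1:1 fashion" (Section 10.6.1). For the primary contrast, "the estimated power with 20 patients in each arm (40 patients total) would be 71% to 96" percent (Section 10.5). That figure rests on the statements that "patients perform approximately 18%, 51%, 26%, and 48% worse post-TIPS" on single tests and that "test performance is unchanged in the discontinuation arm".

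**Step 1: the plan's own power.** No SD is given for the change score, so 71% to 96% cannot be reproduced forward. It can be solved backwards. For a two-sided t-test with 20 per arm, the degrees of freedom are 38 and the noncentrality is d × √(20/2), where d is the arm difference in SD units. Power of 71% needs d = 0.82, and 96% needs d = 1.20.

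**Step 2: the two rules side by side.** In these linear models c − c' = a×b. The comparison of c' with c in Section 10.2 is therefore a statement about the indirect effect, which is what the bootstrap tests. Sections 10.4.3 and 2.2 add c ≠ 0. If all three are tested, P(c, a and b all significant) ≤ P(c significant). On the plan's own assumptions the ceiling is 71% to 96%.

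**Step 3: the size of the loss.** The documents give no path sizes. Assume a = 1, b = 0.6, residual SD 1 for taxon and PHES, normal errors, complete data, 40 patients, one taxon and no false discovery rate correction. The within-arm SD of the PHES change is √(1 + 0.6²) = 1.166, so d = (c' + 0.6)/1.166. Varying the direct effect c' moves the total effect and leaves a×b unchanged.

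| c' | d | Power for c | Bootstrap of a×b | c, a and b all significant | Retained |
|---|---|---|---|---|---|
| 0.80 | 1.20 | 96% | 82% | 80% | 80/82 = 98% |
| 0.36 | 0.82 | 71% | 83% | 62% | 62/83 = 75% |
| 0 (complete mediation) | 0.51 | 36% | 82% | 32% | 32/82 = 39% |
| −0.40 (opposing) | 0.2/1.166 = 0.17 | 8% | 82% | 7% | 7/82 = 9% |

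These are simulated. Repeat runs of 1,500 to 3,000 trials with 800 percentile-bootstrap draws agree to within two points.

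**Step 4: other path sizes** (4,000 trials, 1,000 draws; bootstrap alone against bootstrap plus a significant c).
- Near the lower planned effect (d = 0.81): 42% vs 33%, 71% vs 53%, 89% vs 65%.
- Near the upper planned effect (d = 1.17): 43% vs 41%, 73% vs 70%, 89% vs 85%. Over both, the relative loss is about 3% to 26%.
- Complete mediation, d from 0.28 to 0.60: 44% vs 8% up to 88% vs 41%. At d = 0.77 it is 94% vs 62%.

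**Step 5: multiplicity.** The number of taxa is not stated. As a rough and conservative stand-in for Benjamini-Hochberg with one true mediator, apply a Bonferroni-level threshold and use joint significance of a and b as a proxy for the bootstrap. With a = 1 and b = 0.6, power without any condition on c falls from 81% to 41% (10 taxa), 17% (50) or 11% (100). At d = 0.82 with 50 taxa, adding the condition on c changes 17% to 15%.

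**Step 6: error rate without the condition on c.** Bootstrap type I error was 5.6% with b = 0, 5.5% with a = 0 and 0.3% with both zero. The highest value in any null setting run was 7.7% (1,000 trials).

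**The case against.** Four objections deserve weight.

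- **The 0.05 test of c is inferred.** Section 10.4.3 states conditions on coefficients and Section 2.2 speaks of causal relations. Neither says that c must reach p < 0.05 before a taxon is examined. This stands, and the cap is therefore conditional on that reading. It is a natural reading, because Section 10.4.1 applies 0.05 to all inferential tests and Section 10.4.3 says the relationships will be formally tested.
- **At the planned effect the loss is modest.** A reader might infer that the three-part rule generally throws away most of the bootstrap's power. The documents do not support that. Section 10.5 plans for 71% to 96% power on c, and at those effects the loss is between a few percent and about a quarter.
- **Multiplicity and sample size matter more at the planned effect.** A reader might also infer that the condition on c, not the 40 patients, explains most of the low power that Section 10.4.11 admits. Step 5 contradicts this.
- **Requiring c is a defensible cautious choice.** The exploratory objective in Section 3 asks whether an existing relationship runs through the microbiome, which presupposes a total effect. This supports careful interpretation when c is not significant. It does not explain why Section 10.2 omits the condition.

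Against the second point, the planned effect may be optimistic. Section 10.5 assumes no worsening at all in the discontinuation arm and makes no dropout allowance. Section 7.5 permits on-demand PPIs, lactulose and rifaximin, any of which could shrink c.

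**Conclusion.** The point holds as an inconsistency with a bounded cost. Sections 2.2 and 10.4.3 require c ≠ 0, Section 10.2 does not, and the named bootstrap does not need it. If c is tested at 0.05, the ceiling on detection is exact and common to all taxa.

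With a = 1 and b = 0.6, the power lost is about 2 points at d = 1.20 and about 21 points (a quarter) at d = 0.82. Among these scenarios it exceeds half only when the total effect is well below plan (d = 0.51) or a direct effect opposes the indirect one. These figures rest on assumed path sizes, normal errors, complete data, a single non-compositional taxon and no false discovery rate correction. Correction and missing stool samples would lower all the absolute powers.

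The endpoint is exploratory and the primary analysis is untouched, so this is a worthwhile improvement and not a serious defect.

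**What to change.** - In Sections 2.2 and 10.4.3, delete c ≠ 0 as a requirement for calling a taxon a mediator.
- Align the rule with Section 10.2: declare a mediator on the bootstrap test of the indirect effect (a×b = c − c'), estimated within the compositional mediation model that Section 10.4.3 names. Section 10.2 writes c' < c as a one-directional inequality, so state that the test is two-sided, as in Section 10.4.1.
- Define how the bootstrap p-value is computed, and send those p-values to the Benjamini-Hochberg step.
- Report c, a, b and c' with confidence intervals, and say that mediation will be interpreted cautiously when c is not significant.

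**Cost.** No new data and no change to the primary analysis. Section 10.1 says there is no separate SAP, so this is a protocol amendment that needs IRB approval under Section 13.2. The statistical downside is a bootstrap type I error that may sit slightly above 5% with 40 patients, which is acceptable for an endpoint already labelled exploratory.
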